#### 4.4.e. Measures:

**Screening:** The eligibility screener will assess age, CCS status ("Are you currently registered for classes at a community college?"), recent heavy drinking ("How often in the past two weeks have you had 4[5] drinks in one sitting?"), 114,115 mobile phone use ("Do you have a smartphone?"), and comfort reading English ("How comfortable are you reading English?"). Individuals with a score >14 on the Alcohol Dependence Scale, 116,117 and respondents who answer "Yes" to the question "Have you ever been treated for an alcohol problem?" will be excluded (see section 4.3. for inclusion/exclusion criteria).

**Demographics:** Participants will indicate their age and gender, race, ethnicity, education level, weight (for estimating BAC), marital status, parental status (presence and number of minor children, whether living with them), employment (none/part-time/full-time; number of hours/week), and household income.

**Alcohol Use (Aim 2.1):** The definition of a standard alcohol drink will be provided for all assessments as a 12-ounce beer or wine cooler, a 5-ounce glass of wine, one mixed drink, or 1 shot (1.5 ounces) of liquor. The Timeline Follow-back (TLFB) a self-administered, well-validated, calendar-assisted measure that collects participants' retrospective account of drinking behavior,  will be used to construct our primary

outcome of number of heavy drinking days over the past 3 months. The Brief Young Adult Alcohol Consequences Questionnaire (BYAACQ) is a 24-item measure of negative consequences due to alcohol over the past 3 months; items are summed for a total score. Secondary outcomes: We will use the TLFB to calculate the number of drinking days, number of drinks per week, and eBAC. The AUDIT-C will be used to assess hazardous drinking at screening and all follow up assessments.

During the 12-week intervention, we will also use "push" text messaging to deliver weekly assessments of drinking to all study participants (both arms). These messages will be used to collect single-item weekly assessments of HD episodes (e.g., "Did you drink 4 drinks [5 drinks] in a day over the past week? Please text back 'YES' or 'NO'"), and maximum alcohol use ("What is the highest number of alcohol drinks you had in a day over the past week?"). We had a 94% response rate to this type of assessment in our pilot.

Measures for Secondary effects of CARES: In addition to direct effects on alcohol use, other alcohol-related factors will be assessed to strengthen the need for the CARES program and for future marketing efforts. We will assess self-efficacy for resisting drinking using the Brief Situational Confidence Questionnaire (8 items). 111,126 Motivation to reduce alcohol use will be assessed using the Readiness to Change Questionnaire (12 items; 5-point scale ranging from strongly disagree to strongly agree). 127 Use of protective strategies will be measured with the 15-item Protective Behavioral Strategies Survey, 83,84 that has three subscales: Manner of Drinking, Limiting Drinking, and Harm Reduction that was developed for use among college students (5-point scale ranging from never to always). Risk perception will be assessed using the Alcohol Effects Questionnaire (AEQ), a 40-item measure used to assess positive and negative alcohol-related expectancies (6-point scale ranging from strongly agree to strongly disagree). 128

**Moderators (Aim 2.2):** Assessments of demographics (e.g., gender, age, race/ethnicity, parental status, employment) and heavy drinking are described above and will be investigated as potential moderators of intervention efficacy.

CARES-Specific Processes (Aim 2.3): To investigate engagement with the CARES app we will ask CARES participants to rate their liking of each text message they receive using a 5-point scale. The app will also calculate the time to respond (i.e., latency) to this rating request. We will also collect information about the sharing of texts through the app and through a survey at week 12 ("Did you share any of the CARES messages with your friends or family?"). The content of the text messages will be coded according to the constructs identified in Table 2, and associations with liking, sharing, and weekly outcomes will be evaluated. We will also assess the same User Engagement analytics described above (section 4.3.f). Analyses are described in section 4.4.h.

**4.4.f Methods Used to Achieve Scientific Rigor and Transparency:** We will use multiple methods to ensure an unbiased, rigorous clinical trial. Screening for potential participants will be conducted online with programming to ensure unbiased recruitment results. All data collected in online surveys and through the app are entered by participants, avoiding any potential bias by study staff. Structured interview guides will be used to ensure consistency in Phase I. All Phase II study participants will have the same schedule of assessments to avoid bias due to unequal subject burden or priming effects from multiple assessments (e.g., if delivered unequally between groups). Participants will be randomly assigned to condition via computer algorithms. Analyses will follow the plans developed a priori. Statistical power is conservatively estimated based on effect sizes from relevant literature and our pilot work, and recruitment goals are set to allow for reasonable attrition. To ensure transparency, terms, our study will be registered on ClinicalTrials.gov in advance of collecting data.

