## 4.3.b. Inclusion/Exclusion Criteria:

(1) age 18-29; (2) current CCS; (3) report ≥ two heavy (episodic) drinking (HEDs) in the past two weeks (This pattern is called Frequent Binge Drinking and should net a group of regular heavy drinkers); (an HED is defined as 5 [4] or more drinks in one sitting for men [women]); (4) has a smartphone and uses apps and text messaging; and (5) speaks and reads English comfortably.

Due to safety concerns, we will exclude participants who (1) receive a score >14 on the Alcohol Dependence Scale (indicating psychological to physical dependence), 116,117 or (2) report prior or current alcohol treatment (these individuals will be provided information about local treatment options).

- 4.3.c. Recruitment Procedures: Participants will be recruited through flyers, classroom presentations, and emails to students at CCRI and BCC. Ads will provide a brief description of the study, a study website and a contact phone number, allowing individuals to access information about the study by phone or internet. These recruitment and enrollment procedures have been used successfully in our previous studies. 16,18 Recruitment materials will emphasize that professors and community college administrators will not have access to information about participants. The website will provide a description of the study and an option to continue to online screening questions. For those calling by phone, study staff will briefly explain the study, answer questions, and direct interested callers to the website to complete screening. At the end of the screening survey, respondents will be asked to provide their community college email address. Our web-based survey system will be programmed to determine the eligibility of respondents, check the provided email address against prior respondents, and send the eligibility information only to valid email addresses (e.g., ccri.edu or bcc.edu) that have not previously been used. These procedures ensure that respondents will not be able to complete the screener more than once. Email addresses will be stored in a separate data table from screening responses (linked by a unique ID), allowing us to maintain confidentiality.

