Aim 2.2. Moderation Effects: There has been limited exploration of individual- and intervention-related factors that may moderate the efficacy of mHealth interventions. We will examine demographic factors (e.g., gender, age) as moderators of the intervention. The extent to which demographics that tend to be different from traditional 4-year college students, including race/ethnicity, marital and parental status, employment (full/part-time, hours worked/week), and level of heavy drinking at baseline (defined as 5 [4] drinks on a single occasion for men [women] in the past 30 days) will also be examined as moderators of the intervention. Moderation analyses will be conducted by adding these variables to the mixed effects regression models; the main effect of each potential moderator and the interactions between that moderator and intervention condition will be assessed (group × moderator × time).

Aim 2.3 Predictors of CARES outcomes (Exploratory Aim): Among those receiving CARES, additional analyses will examine trends over time in the weekly (12 weeks) TxM responses to questions asking: (1) whether the participant had engaged HD that week (yes/no) and (2) the highest number of alcohol drinks in a day over the past week. Analyses will examine participant ratings of received texts, latency of response and self-reports of any sharing of texts (section 4.4.e), to examine whether individual responses to each message or type of message (thematic content) are predictive of alcohol use. Analyses of these data will use mixed effects regression modeling approaches to evaluate the effect of time on each outcome, estimating a binomial model for the dichotomous outcome of HD and a Poisson model for the count variable of maximum number of drinks, each of which uses a logit link function.

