**Additional Analyses:** Across all aims, we will extend the examination of intervention comparisons to additional alcohol outcomes (e.g., number of drinking days, number of drinks per week). Data on alcohol use collected at the weekly level (any heavy drinking and maximum number of drinks on a single day over the past week) will be used in ancillary analyses to investigate trajectories in heavy and peak drinking episodes. Analyses will use mixed effects regression modeling approaches to evaluate the effect of time on each outcome, estimating a binomial model for the dichotomous outcome of HD and a Poisson model for the count variable of peak drinks, each of which uses a logit link function.

**Missing Data:** All analyses will be based on an intent-to-treat approach meaning that all participants will be included in the analyses regardless of completeness of data. Our proposed sample size allows for up to 20% attrition at 6-months (see Power Analysis). We will test for systematic differences between participants who do and do not complete assessments to determine the nature of any potential bias due to attrition. Full-information maximum likelihood (FIML) methods will be used in our analyses and we will supplement with multiple imputation (MI) as needed.  To support missing-at-random assumptions required for unbiased

interpretation of FIML and MI estimates in mixed effects regression models (e.g., Proc MIXED) we will run sensitivity analyses. If the results of the sensitivity analyses are similar with and without missing data substitution, confidence in the findings increases.

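### The weekly heavy-drinking text asks only YES/NO, which the peak-drinks text already implies, and never asks how many heavy days; falls are registered, but attenuated (minor)

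*Combined protocol and SAP*

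**What the plan says.** Section 4.4.e uses push texts "to deliver weekly assessments of drinking to all study participants (both arms") over the 12 weeks. Two items are sent:

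- heavy drinking: "Did you drink 4 drinks [5 drinks] in a day over the past week? Please text back" YES or NO;
- peak drinking: "What is the highest number of alcohol drinks you had in a day over the past week".

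Section 4.3.f carries the same pair for Phase I. In section 4.4.h, Aim 2.3 (labelled exploratory, CARES arm only) analyses "whether the participant had engaged HD that week (yes/no") with a binomial model and peak drinks with a Poisson model. Under Additional Analyses, the weekly data "will be used in ancillary analyses to investigate trajectories in heavy and peak drinking episodes", with the same two models.

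Three other provisions matter. The heavy-drinking threshold is fixed by gender: "an HED is defined as 5 [4] or more drinks in one sitting for men [women"). Gender is collected: "Participants will indicate their age and gender". Entry requires that participants "report ≥ two heavy (episodic) drinking (HEDs) in the past two weeks". The primary outcome, the number of heavy drinking days over three months, comes from the TLFB and not from these texts.

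**The concern.** The two weekly items overlap, and the quantity of most interest is missing. Both cover the past week and both refer to drinks in a day, so the YES/NO reply is a dichotomised form of the peak-drinks reply. Section 4.4.h nevertheless models them as two outcomes. Neither says how many heavy days there were.

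Participants enter at an average of at least one heavy episode per week, a range in which a YES/NO item starts to saturate. The programme aims at harm reduction rather than abstinence (section 4.2.b), so a partial fall, such as three heavy nights to one, is a result it seeks. That fall is invisible within a week. At stake is the precision of the week-level analyses under Aim 2.3 and of the ancillary trajectories, which would describe weeks with any heavy drinking rather than the frequency of heavy drinking.

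**Working it through.** **Plan's own figure.** The only design calculation is for the primary outcomes (section 4.4.h, Power Analysis). With d = 0.41, power 0.80 and alpha 0.05 (two-sided assumed), a noncentral-t calculation gives 95 per arm (power 0.803); 95/0.80 rounds up to 119 per arm, 238 in all. It reproduces and is unaffected. No calculation is given for the weekly texts.

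**Redundancy.** Same window, same unit, gender known. YES holds exactly when peak is at least 4 (women) or at least 5 (men). Given consistent replies to both texts, the YES/NO item adds nothing.

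**What a single week can show.** Falls of 4 to 2, 3 to 1 or 2 to 1 read YES before and after. A fall to zero is recorded.

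**Room to fall at entry.** With k heavy days spread at random over 14 days, P(YES in a given week) = 1 - C(7,k)/C(14,k).
- k = 2: 1 - 21/91 = 76.9%
- k = 3: 90.4%
- k = 4: 96.5%

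**Information within a person.** Assume weekly heavy days are Poisson with rate λ. Then P(YES) = 1 - exp(-λ), and YES/NO keeps λ/(exp(λ) - 1) of the count's information on the log rate.

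| λ per week | P(YES) | YES weeks in 12 | Information kept |
|---|---|---|---|
| 1 | 63.2% | 7.6 | 58% |
| 1.5 | 77.7% | 9.3 | 43% |
| 2 | 86.5% | 10.4 | 31% |
| 3 | 95.0% | 11.4 | 16% |

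Halving the rate from 2 to 1 (24 to 12 expected days) shows as 10.4 to 7.6 YES weeks, a 27% fall in place of 50%.

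**Between-person spread.** The ratios above ignore variation between people, which dilutes the practical loss. Under a gamma-Poisson model, shape = mean²/(SD² - mean), whatever the recall window. From the pilot (section 4.2.d, heavy drinking episodes):
- post-intervention, control: 4.07²/(4.29² - 4.07) = 1.16
- post-intervention, intervention: 2.39²/(2.35² - 2.39) = 1.82
- week 12, control: 4.66²/(5.30² - 4.66) = 0.93
- week 12, intervention: 2.06²/(2.10² - 2.06) = 1.81

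**Power if the arms were compared.** Simulation with 125 per arm, 12 weeks, a true 15% reduction and days capped at 7; t-test on the square root of the 12-week count versus the number of YES weeks. At 1 to 2 heavy days per week:
- shape 1.8: 33-36% (count) vs 25-29% (YES/NO)
- shape 0.93: 19-20% vs 15-17%

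Allowing rates up to 3 per week, the gap runs from about 3 to 13 points.

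**At the pilot's own week-12 means.** The recall window is not stated, so a range is shown. Standardised arm difference over 12 weeks:

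| Assumed window | Count | YES weeks |
|---|---|---|
| 2 weeks | 0.73 | 0.44 |
| 4 weeks | 0.71 | 0.58 |
| 6 weeks | 0.70 | 0.63 |
| 13 weeks | 0.65 | 0.63 |

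**The case against.** The strongest reply is that little depends on these texts. The TLFB is calendar-assisted and at month 3 covers the same 12 weeks, so the number of heavy days is already measured in both arms. The weekly data feed an aim labelled exploratory and analyses labelled ancillary. Section 4.4.h models the effect of time on the weekly items and specifies no arm contrast for them, so the power figures describe an analysis the plan does not commit to. For a large effect the item copes: with a 40% reduction, 100 per arm and shapes 0.93 to 1.8, YES/NO power is 73-97% against 86-99% for a count. All of this stands, and it sets the priority.

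A reader might also infer three stronger things that the documents do not support:

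- *That the item cannot register falls in heavy days.* YES weeks do fall with the rate, and at the entry minimum about 23% of weeks are already NO if the days fall at random. Entry at one per week is a two-week average; both episodes may lie in one week.
- *That the item is worthless.* It could serve when the peak text is unanswered or as a consistency check, although no such purpose is stated.
- *That the power loss is 10 to 20 points.* That needs a gamma shape of about 4; the pilot figures imply 0.93 to 1.82. The pilot admitted people with one episode in two weeks, so the spread here could be somewhat narrower, but nothing in the documents points to 4.

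Finally, the YES/NO wording is introduced as an example. That does not remove the point, because section 4.4.h separately fixes a dichotomous weekly outcome.

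**Conclusion.** The point holds as a minor measurement weakness. The YES/NO text largely duplicates the peak-drinks text, and the weekly number of heavy days is not collected by text. Reductions are seen in attenuated form, most weakly among people with about three or more heavy days per week. Under Poisson counts the item keeps about 58% of the within-person information at 1 heavy day per week and 31% at 2; with pilot-like spread, the power cost for a 15% arm difference would be about 3 to 13 points, and neither version would be well powered for so small an effect.

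These sizes rest on assumptions the documents do not settle: Poisson or gamma-Poisson counts, an unstated weekly rate (1 to 3 tried), an unstated pilot recall window, and an arm comparison that is not planned. The redundancy and the within-week blindness need none of them. The primary outcomes, sample size and main conclusions are unaffected.

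**What to change.** Before Phase II enrolment, replace the YES/NO text in section 4.4.e (and its twin in 4.3.f) with: *On how many days in the past week (0-7) did you have [threshold] or more drinks?* Keep the peak-drinks text. In section 4.4.h, under Aim 2.3 and Additional Analyses, model heavy days per week as a 0-7 count; derive any-versus-none from it if still wanted.

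The cost is one reworded automated text and one changed outcome line in each of the two analysis paragraphs. The number of texts stays the same, and the companion text already needs a numeric reply. The downside is slightly more effort per reply, and the 94% pilot response rate was observed for the existing type of item, so response to the new one should be monitored.

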#### 4.4.g. Design Considerations:

Alternative Designs Considered: The issue of greatest importance in designing this study was to rigorously evaluate CARES compared to a control. In this regard, we deemed it important that the comparison condition was ecologically valid (comparable to CARES in accessibility) and provided a reasonable real-world comparison. In particular, for future commercialization efforts, it is important that we compare our CARES app to a program that any community or technical college would see as a viable alternative to purchasing CARES. Thus, an online (or app delivered) format was important, and that it be free or low-cost. That is, why would they purchase CARES if they could get an alternative, easily accessible (i.e., online or app) program free?

We considered a comparison with a 'no-intervention' control (e.g., assessment only or a wait-list) but a no-intervention control seemed to be a bit of a 'straw-man' in that, given our pilot data, CARES is likely to easily outperform nothing. Also, we wanted a more real-world comparison, so we chose a control group using an alcohol program that is free, inexpensive and easily disseminated, and thus, something a community college might consider as an alternative to purchasing CARES.

We considered other web-based college alcohol interventions including AlcoholEdu (everfi.com), College Drinkers Check-up (CDCU; collegedrinkerscheckup.com), and e-Checkup-to-go (eChug). However, the CDCU has only one peer-reviewed publication describing two small randomized trials that support its efficacy. AlcoholEdu has several peer-reviewed evaluations, but can cost \$10,000 or more per school per year. Neither eChug nor AlcoholEdu were designed for, or tested in, community college students. We could have proposed to compare CARES to another text-messaging-based alcohol intervention program without an app feature, but as with the aforementioned CDIs, these programs were not designed for, and have not been

tested in, CCS We also considered comparing to the 'gold standard' of a Brief Motivational Interview, a well-established intervention for college students.  Brief motivational interviews have a low likelihood of being adopted by community colleges, which typically do not have the resources to support in-person counseling,  and thus, could not be delivered to all CCS who drink. Ecological validity and disseminability were high priorities in the development of CARES and in the consideration of the other conditions.

**4.4.h Statistics Procedures and Data Analyses:** [name] will conduct all statistical analyses. **Preliminary Analyses:** Prior to conducting the main analyses, the distribution of all outcome variables will be examined. While count-based outcomes are expected to follow Poisson or negative binomial distributions, and the main analyses will be conducted using counts, we also can create dichotomous variables indicating whether participants engaged in any (vs no) HD and/or experienced any (vs no) problems. This will allow us to evaluate the extent to which there is clinically meaningful change in important public health outcomes. Baseline comparisons between CARES and CYD on demographic and alcohol use variables will be assessed using chi-square and t-tests. Any group differences will be statistically controlled for in the main analyses as a subject- (e.g., gender) or time- (e.g., number of HD days) dependent covariates, as appropriate.

Aim 2.2. Moderation Effects: There has been limited exploration of individual- and intervention-related factors that may moderate the efficacy of mHealth interventions. We will examine demographic factors (e.g., gender, age) as moderators of the intervention. The extent to which demographics that tend to be different from traditional 4-year college students, including race/ethnicity, marital and parental status, employment (full/part-time, hours worked/week), and level of heavy drinking at baseline (defined as 5 [4] drinks on a single occasion for men [women] in the past 30 days) will also be examined as moderators of the intervention. Moderation analyses will be conducted by adding these variables to the mixed effects regression models; the main effect of each potential moderator and the interactions between that moderator and intervention condition will be assessed (group × moderator × time).

Aim 2.3 Predictors of CARES outcomes (Exploratory Aim): Among those receiving CARES, additional analyses will examine trends over time in the weekly (12 weeks) TxM responses to questions asking: (1) whether the participant had engaged HD that week (yes/no) and (2) the highest number of alcohol drinks in a day over the past week. Analyses will examine participant ratings of received texts, latency of response and self-reports of any sharing of texts (section 4.4.e), to examine whether individual responses to each message or type of message (thematic content) are predictive of alcohol use. Analyses of these data will use mixed effects regression modeling approaches to evaluate the effect of time on each outcome, estimating a binomial model for the dichotomous outcome of HD and a Poisson model for the count variable of maximum number of drinks, each of which uses a logit link function.

**Additional Analyses:** Across all aims, we will extend the examination of intervention comparisons to additional alcohol outcomes (e.g., number of drinking days, number of drinks per week). Data on alcohol use collected at the weekly level (any heavy drinking and maximum number of drinks on a single day over the past week) will be used in ancillary analyses to investigate trajectories in heavy and peak drinking episodes. Analyses will use mixed effects regression modeling approaches to evaluate the effect of time on each outcome, estimating a binomial model for the dichotomous outcome of HD and a Poisson model for the count variable of peak drinks, each of which uses a logit link function.

**Missing Data:** All analyses will be based on an intent-to-treat approach meaning that all participants will be included in the analyses regardless of completeness of data. Our proposed sample size allows for up to 20% attrition at 6-months (see Power Analysis). We will test for systematic differences between participants who do and do not complete assessments to determine the nature of any potential bias due to attrition. Full-information maximum likelihood (FIML) methods will be used in our analyses and we will supplement with multiple imputation (MI) as needed.  To support missing-at-random assumptions required for unbiased

interpretation of FIML and MI estimates in mixed effects regression models (e.g., Proc MIXED) we will run sensitivity analyses. If the results of the sensitivity analyses are similar with and without missing data substitution, confidence in the findings increases.

Power Analysis: The proposed study is fully powered for our primary outcomes of heavy (episodic) drinking and alcohol-related problems. Results from our pilot study (section 4.2) indicated a d of 0.64 (95% CI = 0.13, 1.16) for heavy (episodic) drinking and 0.21 (95% CI = -0.32, 0.75) favoring the intervention at the 12week assessment (6-weeks post-intervention). When we assessed the presence (any) or absence (none) of alcohol-related problems at the 12-week assessment, we found a d of 0.66 (95% CI = 0.14, 1.18) favoring the intervention. Findings from a related pilot trial evaluating an extended internet-based intervention that included text messages (AHC; AlcoholHelpCenter.net) compared to CYD indicated a d of 0.41 (95% CI = 0.11, 0.72) on the Alcohol Use Disorders Identification Test for Consumption (AUDIT-C) at the 6-month follow-up. (The AUDIT-C is a brief screening measure used to assess hazardous drinking, including heavy drinking, and higher scores would indicate that the individual would likely be experiencing alcohol-related problems.) Therefore, we conservatively chose to power on a d of 0.41 across the 3- and 6-month assessments. This effect size is considered to be small to medium using Cohen's criteria. 136 It is important to note that our power analysis is based on our ability to detect differences in at-risk drinking between our two active conditions, CARES and CYD, across a 6-month follow-up. Given the aforementioned findings, and an alpha level of 0.05 and power of 0.80, a power analysis was conducted using GPower 3.0.137 This analysis revealed that 190 participants (95 per condition) would be required. Assuming an estimated attrition of 20% by the 6-month follow-up, approximately 238 participants (119 per condition) are needed. Thus, our proposed sample size of 250 (125 participants per group) will be sufficient to detect even small between-group effects on the hypothesized outcomes as well as controlling for covariates.

